6.2. Exclusion Criteria

1. Treatment with chemotherapy (not including Tyrosine Kinase Inhibitors) or radiotherapy within 4 weeks (6 weeks from nitrosoureas or mitomycin C), or treatment with monoclonal antibody therapy within 4 weeks prior to start of study treatment.

Note: No minimum washout period is required for tyrosine kinase inhibitor therapy (eg, imatinib or sunitinib).

- 2. Patients must have recovered from adverse events (greater than grade 1) due to prior anticancer therapy, except for stable chronic toxicities such as alopecia.
- 3. Participation in any other clinical study with investigational drug received within 28 days or 5 half lives (whichever is longer) before first dose.
- 4. Subjects who have received prior anti-PD-1 or anti-PD-L1 antibody, or an IDO inhibitor. Subjects who have received experimental vaccines or other immune therapies should be discussed with the principal investigator to confirm eligibility.
- 5. Any prior ≥ Grade 3 immune-related adverse event (irAE) while receiving immunotherapy, or any unresolved irAE > grade 1.
- 6. Subjects receiving immunologically based treatment for any reason, including chronic steroids or prednisone (at dose >10 mg/day of prednisone) within 14 day prior to first study treatment. Inhaled or topical steroids or systemic steroids (at dose ≤10 mg/day of prednisone) is permitted.

Version Date: 11/09/2017

- 7. Subjects with any active or inactive autoimmune process (eg, rheumatoid arthritis, moderate or severe psoriasis, multiple sclerosis, inflammatory bowel disease) or who are receiving systemic therapy for an autoimmune disease. Exceptions include vitiligo, hypothyroidism controlled on hormone replacement, type I diabetes, Grave's disease, adrenal insufficiency on stable replacement doses of steroids (prednisone ≤10 mg/day or equivalent), or with principal investigator approval.
- 8. No prior organ allograft or allogenic bone marrow transplantation.
- 9. History of (noninfectious) pneumonitis that require steroids or current pneumonitis.
- 10. A diagnosis of another active malignancy with the following exceptions: basal or squamous cell carcinoma of the skin, in-situ carcinoma of the cervix, isolated elevation of prostate-specific antigen, indolent secondary malignancies not requiring active therapy, or with the approval of the principal investigator. Subjects with a completely treated prior malignancy and no evidence of disease for ≥ 2 years are eligible.
- 11. Subjects with known active hepatitis B (HBV) or hepatitis C (HCV) infection as defined by the following (Hepatitis screening studies are required (see section 13)):
 - Positive test for hepatitis B surface antigen
 - Positive test for hepatitis C antibody and/ or hepatitis C quantitative viral load (Note: Subjects with a positive hepatitis C antibody and negative quantitative hepatitis C PCR viral load are eligible)
- 12. Subjects with a known history of HIV, including patients with controlled disease on antiretroviral therapy. HIV testing is not required as part of screening for this study.
- 13. Subjects receiving MAO inhibitors within 21 days of study enrollment (epacadostat increases serotonin levels, theoretically increasing the risk of serotonin syndrome, although this has not been reported in any ongoing clinical studies to date).
- 14. Any history of serotonin syndrome (SS) after receiving 1 or more serotonergic drugs.
- 15. Current pregnancy or breast feeding. Pregnant women are excluded from this study because the teratogenicity of epacadostat and pembrolizumab are unknown. Because there is an unknown but potential risk for adverse events in nursing infants secondary to treatment of the mother with pembrolizumab and/or epacadostat, breastfeeding should be discontinued in all female subjects.
- 16. Receipt of live attenuated vaccines (including, but not limited to: intranasal influenza vaccine (FluMist), measles, mumps, rubella, chicken pox, yellow fever, rabies, Bacillus

Version Date: 11/09/2017

Calmette-Guerin (BCG), and typhoid vaccine) within 30 days before the first dose of study treatment.

- 17. Concurrent use of any medication that is an inhibitor of UGT1A9 (section 8.3.2) during the screening or treatment period.
- 18. Major surgical procedure or significant traumatic injury within 14 days of initiating study drug or anticipation of the need for major surgery during the study.
- 19. Inability to swallow capsules, or refractory nausea and vomiting, malabsorption, an external biliary shunt, or significant bowel resection that would preclude adequate absorption.
- 20. Uncontrolled intercurrent illness including, but not limited to, ongoing or active infection, active liver disease, symptomatic congestive heart failure, unstable angina pectoris, cardiac arrhythmia, or psychiatric illness/social situations that would limit compliance with study requirements.
- 21. History of current evidence of any condition, therapy, or laboratory abnormality that might confound the results of the study, or interfere with the subject's participation for the full duration of the study.
- 22. Known allergy or reaction to any component of either study drug formulation.

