8.3.2. Prohibited Medications and Measures

Subjects are prohibited from receiving the following therapies during the screening and treatment phase of this study unless otherwise noted below:

- Any investigational medication other than the study drugs.
- Any anticancer medications, including chemotherapy or biologic therapy other than the study medications.
- Any immunological-based treatment for any reason.
 - Note: Inhaled or topical steroids are allowed, and systemic steroids at doses ≤ 10 mg/day prednisone or equivalents are allowed, and immune suppressants are allowed for treatment for immune toxicities.
- Radiation therapy
 - O Note: Radiation therapy to a symptomatic solitary lesion or to the brain may be allowed after consultation with the principal investigator.
- Live Administration of live attenuated vaccines within 30 days before the first dose of study treatment and while participating in the study is prohibited. Examples of live vaccines include, but are not limited to, the following: measles, mumps, rubella, chicken pox, yellow fever, rabies, BCG, and typhoid vaccine. Seasonal influenza vaccines for injection are generally killed virus vaccines and are allowed; however, intranasal influenza vaccines (eg, FluMist®) are live attenuated vaccines and are not allowed.
- Any melatonin supplements.
- Any MAOI or drug associated with significant MAO inhibitory activity agents is prohibited from 21 days before Day 1 through 2 weeks after the final dose of epacadostat has been taken (see Appendix C).

Version Date: 11/09/2017

- Any UGT1A9 inhibitor, including acitretin, amitriptyline, androsterone, cyclosporine, dasatinib, diclofenac, diflunisal, efavirenz, erlotinib, estradiol (17-beta), flutamide, gefitinib, gemfibrozil, glycyrrhetinic acid glycyrrhizin, imatinib, imipramine, ketoconazole, linoleic acid supplements, mefenamic acid, mycophenolic acid, niflumic acid, nilotinib, phenobarbital, phenylbutazone, phenytoin, probenecid propofol*, quinidine, ritonavir, sorafenib, sulfinpyrazone, valproic acid, and verapamil.
 - *Note Propofol, when used for short-term sedation during surgical/biopsy procedures, is allowed after consultation with the principal investigator. The epacadostat dose may be taken on the morning of the procedure, and the evening dose held following the procedure. Epacadostat may be resumed the next day.

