12. STUDY EVALUATIONS

12.1. Screening Phase

The screening phase will be up to 28 days. Screening is the interval between the signing of the informed consent form (ICF) and the day the subject receives the first dose of treatment in the study (Cycle 1 Day 1). Informed consent must be obtained before performing any study-specific procedures not considered standard of care. Assessments that are required to demonstrate eligibility may be performed over the course of 1 or more days during this phase.

Results from the screening visit evaluations will be reviewed to confirm subject eligibility before enrollment or the administration of study drug. Tests with results that fail eligibility requirements may be repeated during the screening phase if the investigator believes the results to be in error. Additionally, a subject who fails screening may repeat the screening process 1 time if the investigator believes there has been a change in eligibility status (eg, after recovery from an infection).

See Section 13 (table 10-11) for detailed list of screening procedures.

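### The note to exclusion 1 requires no TKI washout and names imatinib, but exclusion 17 with Section 8.3.2 bars imatinib from consent to first dose

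*Combined protocol and SAP*

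**What the plan says.** Four places in the combined protocol and SAP bear on whether a patient may take a tyrosine kinase inhibitor (TKI) between consent and first dose.

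- **Section 6.2, note to exclusion 1**, with the same words under Key Exclusion Criteria in the synopsis: "No minimum washout period is required for tyrosine kinase inhibitor therapy (eg, imatinib or sunitinib"). The note carries no qualification and no cross-reference.
- **Section 6.2, exclusion 17**: "Concurrent use of any medication that is an inhibitor of UGT1A9 (section 8.3.2) during the screening or treatment period".
- **Section 8.3.2**: "Subjects are prohibited from receiving the following therapies during the screening and treatment phase of this study unless otherwise noted below". The UGT1A9 inhibitors that follow include imatinib by name ("glycyrrhetinic acid glycyrrhizin, imatinib, imipramine"), and also dasatinib, nilotinib and sorafenib. The only exception within that list is short-term propofol sedation. A separate bullet bars "Any anticancer medications, including chemotherapy or biologic therapy other than the study medications". The section ends by saying that patients who need a listed treatment should come off the study.
- **Section 12.1**: "Screening is the interval between the signing of the informed consent form (ICF) and the day the subject receives the first dose of treatment". On its length: "The screening phase will be up to 28 days". No minimum is given.

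Inclusion criterion 3a in Section 6.1 requires progression on imatinib, or progression on another TKI for patients who stopped imatinib because of intolerance.

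**The concern.** The note tells a site that a patient may come to first dose straight from imatinib. Exclusion 17, followed through to the list in Section 8.3.2, says that the same patient is ineligible if any imatinib was taken after consent. The drug concerned is the one that generally defines this population, so recent or current use at consent is foreseeable.

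The permissive statement is also the easier one to find. It names imatinib outright, whereas exclusion 17 names no drug and sends the reader to a long list in another section. The synopsis repeats the note, and its key criteria contain no UGT1A9 item.

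Two things are at stake: consistent eligibility handling, and whether a drug on the protocol's own interaction list is taken in the days before epacadostat starts.

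**Working it through.** No published figure needs reproducing. The check sets the rules side by side and applies them to one patient.

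**Inputs**

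- Let *s* be the number of days from consent to first dose. Section 12.1 gives *s* ≤ 28 and no lower bound.
- Let *t* be the number of days from the last imatinib dose to the first study dose.

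**Rules for imatinib**

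| Source | Requirement before first dose |
|---|---|
| Note to exclusion 1 (Section 6.2, synopsis) | *t* ≥ 0: no minimum |
| Exclusion 17 with Sections 8.3.2 and 12.1 | no imatinib after consent: *t* ≥ *s* |

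The two requirements differ by *s* − 0 = *s* days. The largest possible difference is 28 − 0 = 28 days. The smallest is not stated.

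**Patient who continues imatinib after consent and stops just before Cycle 1 Day 1**

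1. Note to exclusion 1: satisfied, because no interval is asked for.
2. Exclusion 17: imatinib is on the Section 8.3.2 list, it was taken between consent and first dose, that interval is screening under Section 12.1, and no exception covers it. The patient fails.
3. Exclusion criteria are cumulative, so the patient is ineligible. The note is then untrue in practice for the drug that it names.

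**Other TKIs**

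- Dasatinib, nilotinib and sorafenib are on the UGT1A9 list. Steps 1 to 3 apply to them unchanged.
- Sunitinib, the note's other example, is not on that list. The Section 8.3.2 bar on other anticancer medication reaches it over the same period. That is a prohibited-medication rule and not a numbered exclusion, so the note's two named drugs are caught by different routes.

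**Patients not affected.** Anyone who stopped the relevant TKI before signing consent satisfies all of these rules.

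**The case against.** The strongest reply is that there is no eligibility contradiction. The note sits under exclusion 1, which sets fixed intervals for chemotherapy, radiotherapy and antibodies, and it can be read as exempting TKIs from those intervals only. Exclusion 17 is a separate concomitant-medication rule, and failing any one criterion excludes the patient. On this view the defect is a missing cross-reference.

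Part of this stands. Read cumulatively, the criteria do give one answer, so a reader who infers that eligibility cannot be determined goes too far. But the note's wording is not limited to exclusion 1 and nothing points to exclusion 17. The cumulative reading settles eligibility only by leaving a plain statement about imatinib that a site cannot safely act on.

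A second reply is that *concurrent* in exclusion 17 means concurrent with epacadostat. That would leave the mention of screening without effect, because under Section 12.1 screening ends at first dose.

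A third reply is that the practical risk is controlled, and this largely stands. Sections 7.1 and 21.5 require central verification of eligibility before treatment, with concomitant medication lists named among the source documents. Section 12.1 allows one repeat of screening when eligibility status is thought to have changed. These safeguards limit the harm, but they act only after the patient has consented and begun screening.

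It is also fair that the synopsis lists only key criteria, so the absence of the UGT1A9 item there is not an error in itself.

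**Conclusion.** The point holds as an inconsistency between stated rules. The note to exclusion 1 gives the wrong answer for a patient who takes imatinib, or another listed TKI, after consent. The two statements differ by the patient's own screening length, at most 28 days.

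This rests on two assumptions: that *screening* in exclusion 17 has the Section 12.1 meaning, and that the note is read as written.

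Two stronger inferences are not supported:

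- **That exclusion 17 imposes a 28-day imatinib washout.** Twenty-eight days is a ceiling on screening. The documents fix no number of washout days.
- **That the trial's statistical conclusions are affected.** The documents do not allow the number of affected patients to be derived, and nothing here changes the two-stage design, its error rates or the rule of at least 3 responses among 21 evaluable patients.

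The consequence is limited to eligibility handling and interacting-drug exposure before first dose. It is worth correcting because the drug is central to the population and the correction is cheap.

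**What to change.** Reconcile the synopsis note, the note to exclusion 1, exclusion 17, Section 8.3.2 and Section 12.1 into one explicit rule for TKI use between consent and Cycle 1 Day 1. State it separately for TKIs listed as UGT1A9 inhibitors and for other TKIs such as sunitinib. Cross-refer the exclusion 1 note to exclusion 17 and Section 8.3.2, and carry the same wording into the synopsis and the eligibility checklist. Which rule stands is for the clinical team to decide.

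The cost is amendment wording and one checklist line. No procedures are added and the sample size does not change.

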6.3. Pregnancy

The effects of pembrolizumab and epacadostat on the developing human fetus are unknown. For this reason, women of child-bearing potential and men must agree to use adequate contraception (Appendix B) prior to study entry and for the duration of study participation. Should a woman become pregnant or suspect she is pregnant while she or her partner is participating in this study, she should inform her treating physician immediately. Men treated or enrolled on this protocol must also agree to use adequate contraception prior to the study, for the duration of study participation, and 4 months after completion of pembrolizumab and/or epacadostat administration.

Sexually active women of child-bearing potential (WOCBP) must use an effective method of birth control during the course of the study, in a manner such that risk of failure is minimized (Appendix B).

Before study enrollment, WOCBP must be advised of the importance of avoiding pregnancy during study participation and the potential risk factors for an unintentional pregnancy. The subject must sign an informed consent form documenting this discussion.

All WOCBP MUST have a negative pregnancy test at the time of study screening. The minimum

Version Date: 11/09/2017

sensitivity of the pregnancy test must be 25 IU/L or equivalent units of HCG. If the pregnancy test is positive, the subject must not receive treatment and must not be enrolled in the study.

In addition, all WOCBP should be instructed to contact the investigator immediately if they suspect they might be pregnant (e.g., missed or late menstrual period) at any time during study participation.

If, following initiation of the investigational product, it is subsequently discovered that a study subject is pregnant or may have been pregnant at the time of investigational product exposure, including during at least 6 half-lives after product administration, the investigational product will be permanently discontinued in an appropriate manner (e.g., dose tapering if necessary for subject safety). The investigator must immediately notify the sponsor of this event and record the pregnancy on the Pregnancy Surveillance Form (not an SAE form). Initial information on a pregnancy must be reported immediately to the sponsor, and the outcome information provided once the outcome is known. Completed Pregnancy Surveillance Forms must be forwarded to Incyte and Merck according to SAE reporting procedures (See Section 10.4.4).

Any pregnancy that occurs in a female partner of a male study participant should be reported to the sponsor. Information on this pregnancy will be collected on the Pregnancy Surveillance Form.

Protocol-required procedures for study discontinuation and follow-up must be performed on the subject unless contraindicated by pregnancy (e.g., X-ray studies). Other appropriate pregnancy follow-up procedures should be considered if indicated. In addition, the investigator must report and follow-up on information regarding the course of the pregnancy, including perinatal and neonatal outcome. Infants should be followed for a minimum of 8 weeks.

6.4. Inclusion of Women and Minorities

Both men and women of all races and ethnic groups are eligible for this trial.

6.5. Subject Recruitment

Patients will be recruited for the study from investigator or co-investigator clinical practices and referring physicians.

6.6. Early Withdrawal of Subjects

6.6.1. When and How to Withdraw Subjects

Patients may withdraw from study at any time. Patients who discontinue early should return within 30 days of the last dose of the study drugs for a follow up evaluation. Any assessments listed for the final visit should be performed at that time.

In addition, any of the following conditions require withdrawal of the subject from study treatment:

Version Date: 11/09/2017

- Disease progression defined by irRECIST criteria
- Lost to follow up or non-compliance with the protocol schedule
- An AE or concurrent illness that in the opinion of the investigator or sponsor warrants the subject's withdrawal from treatment.
- Necessary treatment with other investigational drug or other anticancer medications prohibited by protocol
- Participation in another clinical study using anti-cancer agents
- Request by regulatory agencies for termination of treatment of an individual subject or all subjects under this protocol
- Sexually active subjects who refuse to use medically accepted barrier methods of contraception during the course of the study and for 4 months following discontinuation of study treatment
- Women who are pregnant or are breast feeding
- If the patient withdraws consent for continued participation, he/she will be removed from study.

The reason for study treatment discontinuation will be documented. For subjects who discontinue or are withdrawn from study treatment, every effort must be made to undertake protocol specified follow up procedures and end of treatment assessments, if possible unless consent to participate in the study is also withdrawn.

If a subject is discontinued from study treatment because of an AE considered to be related to study treatment and the event is ongoing 90 days after the last dose of study treatment, the event must be followed until resolution or determination by the investigator that the event has become stable or irreversible.

If a subject withdraws consent to participate in the study the reason for withdrawal will be documented, no further study procedures or assessments will be performed, and no further study data will be collected for this subject other than the determination of survival status from public records such as governmental vital statistics or obituaries.

6.6.2 Data Collection and Follow-up for Withdrawn Subjects

Patients will do off-study visit as long as all toxicity is resolved. The reason for study removal and date the patient was removed must be documented.

7. REGISTRATION PROCEDURES

7.1. CUMC Research Participant Registration

Version Date: 11/09/2017

Confirm eligibility as defined in the section entitled Criteria for Subject Eligibility.

Obtain informed consent, by following procedures defined in section entitled Informed Consent Procedures, along with applicable institutional policies and federal regulations.

Only Investigators/Research personnel properly trained and delegated to consent subjects for this protocol will participate in the consenting process. Furthermore, properly delegated/trained Physician Investigators (e.g., MD, MD/PhD) are required to sign/verify a protocol specific Eligibility Checklist for each subject enrolled on the study, in addition to providing the relevant source documentation confirmation subject eligibility.

All participants must be centrally registered through the Central Registration Office within Herbert Irving Comprehensive Cancer Center at CUMC prior to initiation of study treatment.

Registration hours are available Monday through Friday from 9:00am - 5:00pm EST (excluding holidays and weekends). Same day patient registrations (and after hour registrations) will be accommodated on a case by case basis provided that the study team has expressed all time sensitive registration concerns/cases in a timely manner to the Central Registration Office.

CPDM Central Registration Procedures:

Within 48 hours of obtaining consent (excluding holidays and weekends), a completed/signed IRB approved informed consent HIPAA form, and demographics forms must be submitted to the CPDM Central Registration Office via an email to [contact] or fax to [contact], with the subject line "AAAR1581 Pending Subject Registration Request (PHI)". Upon receipt, applicable subject information as well as a "pending eligibility" status will be entered into HICCC's institutional database. This status will remain until further source documentation is made available to confirm overall patient eligibility. Required materials for all pending registration submissions are as follows:

- Completed/signed IRB approved/stamped Informed Consent Forms, including additional study ICFs for tissue.
- The completed/signed IRB approved HIPAA Authorization form
- Completed/signed CPDM ICF checklist
- Completed/signed HICCC personal census form
- Completed/signed CPDM Demographics Note to File

In order to confirm eligibility status, Investigators/designees (e.g., study specific Clinical Research Coordinator/Research Nurse, etc.) must submit the following documentation to the Central Registration Office via email or fax:

Version Date: 11/09/2017

- The completed/signed study specific Eligibility Checklist (signed by an Physician level Investigator)
- Copies of source documentation necessary for each item to be verified on the CPDM specific Eligibility Checklist, including but not limited to:
 - Ocopy of required laboratory test and procedure reports (e.g., complete blood count, complete metabolic panel, cholesterol and triglycerides pregnancy test when applicable, MRI reports, CT/bone scans, etc.)
 - o Copy of pathology and surgical reports
 - o List of all prior malignancy-directed treatments
 - Ocopy of clinic note(s) or other appropriate medical records capturing the consent process information, along with providing source documentation of any other items needed for screening/eligibility that are not captured in other source document forms (e.g., positive investigator statements of unique eligibility items not captured via other direct source documentation, concomitant medication lists, etc.).
 - o Protocol deviation/waiver approvals (if applicable)
 - o Please note: subject line of email or fax should include the following: "Complete Subject Registration Request (PHI)".

Upon receipt of the above mentioned documentation, participant eligibility information will be verified by a qualified Central Registration Registrar. If any questions arise during the review process, queries in the form of emails will be addressed to the applicable study team personnel for clarification prior to enrollment. All applicable finalized registration/eligibility information will then be entered into HICCC's institutional CTMS database by the Central Registration Registrar. Upon completion, an official subject registration notification email will be sent to the PI/research team which will include eligibility/enrollment status, as well as subject ID information. Protocol therapy may not be initiated prior to receipt of this notification from the Central Registration Office.

All screen fail/ineligible subjects, as well as subject's who withdraw consent prior to enrollment/initiation of protocol therapy must be submitted to the Central Registration office in a manner analogous to the procedures noted above. Applicable source documentation will be required within the corresponding submissions.

